## **5.2 SAFETY PARAMETERS AND DEFINITIONS**

Safety assessments will consist of monitoring and recording adverse events, including serious adverse events and adverse events of special interest, performing protocol-specified safety laboratory assessments, measuring protocol-specified vital signs, and conducting other protocol-specified tests that are deemed critical to the safety evaluation of the study.

Certain types of events require immediate reporting to the Sponsor, as outlined in Section 5.4.

### **5.2.1 Adverse Events**

According to the ICH guideline for Good Clinical Practice, an adverse event is any untoward medical occurrence in a clinical investigation subject administered a pharmaceutical product, regardless of causal attribution. An adverse event can therefore be any of the following:

- Any unfavorable and unintended sign (including an abnormal laboratory finding), symptom, or disease temporally associated with the use of a medicinal product, regardless of whether it is considered related to the medicinal product
- Any new disease or exacerbation of an existing disease (a worsening in the character, frequency, or severity of a known condition), except as described in Section 5.3.5.10
- Recurrence of an intermittent medical condition (e.g., headache) not present at baseline
- Any deterioration in a laboratory value or other clinical test (e.g., ECG, X-ray) that is associated with symptoms or leads to a change in study treatment or concomitant treatment or discontinuation from study treatment
- Adverse events that are related to a protocol-mandated intervention, including those that occur prior to assignment of study treatment (e.g., screening invasive procedures such as biopsies)

### **5.2.2 Serious Adverse Events (Immediately Reportable to the Sponsor)**

A serious adverse event is any adverse event that meets any of the following criteria:

- Is fatal (i.e., the adverse event actually causes or leads to death)
- Is life threatening (i.e., the adverse event, in the view of the investigator, places the patient at immediate risk of death)

This does not include any adverse event that, had it occurred in a more severe form or was allowed to continue, might have caused death.

- Requires or prolongs inpatient hospitalization (see Section 5.3.5.11)

- Results in persistent or significant disability/incapacity (i.e., the adverse event results in substantial disruption of the patient's ability to conduct normal life functions)
- Is a congenital anomaly/birth defect in a neonate/infant born to a mother exposed to study treatment
- Is a significant medical event in the investigator's judgment (e.g., may jeopardize the patient or may require medical/surgical intervention to prevent one of the outcomes listed above)

The terms "severe" and "serious" are not synonymous. Severity refers to the intensity of an adverse event (e.g., rated as mild, moderate, or severe, or according to NCI CTCAE; see Section 5.3.3); the event itself may be of relatively minor medical significance (such as severe headache without any further findings).

Severity and seriousness need to be independently assessed for each adverse event recorded on the eCRF.

Serious adverse events are required to be reported by the investigator to the Sponsor immediately (i.e., no more than 24 hours after learning of the event; see Section 5.4.2 for reporting instructions).

### **5.2.3 Adverse Events of Special Interest (Immediately Reportable to the Sponsor)**

Adverse events of special interest are required to be reported by the investigator to the Sponsor immediately (i.e., no more than 24 hours after learning of the event; see Section 5.4.2 for reporting instructions). Adverse events of special interest for this study include the following:

- Cases of potential drug-induced liver injury that include an elevated ALT or AST in combination with either an elevated bilirubin or clinical jaundice, as defined by Hy's Law (see Section 5.3.5.7)
- Suspected transmission of an infectious agent by the study treatment, as defined below
 

Any organism, virus, or infectious particle (e.g., prion protein transmitting transmissible spongiform encephalopathy), pathogenic or non-pathogenic, is considered an infectious agent. A transmission of an infectious agent may be suspected from clinical symptoms or laboratory findings that indicate an infection in a patient exposed to a medicinal product. This term applies only when a contamination of study treatment is suspected.
- Pneumonitis
- Colitis
- Endocrinopathies: diabetes mellitus, pancreatitis, adrenal insufficiency, or hyperthyroidism and hypophysitis

- Hepatitis, or AST or ALT > 10 × ULN
- Systemic lupus erythematosus
- Neurologic disorders: Guillain-Barré syndrome, myasthenic syndrome or myasthenia gravis, and meningoencephalitis
- Nephritis
- Events suggestive of hypersensitivity, infusion-related reactions, cytokine-release syndrome, influenza-like illness, *and* systemic inflammatory response syndrome
- Ocular toxicities (e.g., uveitis, retinitis, optic neuritis)
- Myositis
- Myopathies, including rhabdomyolysis
- Grade ≥ 2 cardiac disorders (e.g., atrial fibrillation, myocarditis, pericarditis)
- Vasculitis
- Autoimmune hemolytic anemia
- Severe cutaneous reactions (e.g., Stevens-Johnson syndrome, dermatitis bullous, toxic epidermal necrolysis)

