### **3.2 INDEPENDENT DATA MONITORING COMMITTEE**

An iDMC will be convened to evaluate efficacy and safety data during the study. Members of the iDMC will be external to the Sponsor and will follow a charter that outlines their roles and responsibilities. The iDMC will conduct its first review of safety data when 10 patients in the safety run-in have completed at least 1 cycle of study treatment.

On the basis of the different mechanisms of action for each product, the overlapping toxicities of enzalutamide and atezolizumab are thought to not significantly increase the incidence and type of adverse events seen in respective monotherapy studies. In a study investigating enzalutamide in combination with an anti-PD-1 antibody, immune *mediated* toxicities observed were consistent with other studies investigating the anti-PD-1 antibody alone in solid tumors (Graff et al 2016).

The iDMC will specifically evaluate clinically relevant toxicities that are known to be associated with atezolizumab and/or enzalutamide. Refer to [Table 3](#) of the protocol and Section 6 of the Atezolizumab Investigator's Brochure, and enzalutamide local prescribing information. These adverse events include, but are not limited to, the following:

- Gastrointestinal toxicities including diarrhea and immune-*mediated* colitis
- Immune-*mediated* hepatitis
- Immune-*mediated* pancreatitis
- Immune-*mediated* pneumonitis
- Immune-*mediated* endocrinopathies (i.e., diabetes mellitus, hypothyroidism, hyperthyroidism, adrenal insufficiency, and hypophysitis)
- Immune-*mediated* myocarditis
- Neurologic disorders including immune-*mediated* meningoencephalitis, immune-*mediated* neuropathies (i.e., myasthenic syndrome and/or myasthenia gravis, Guillain-Barré syndrome), vertigo and/or dizziness, falls, seizures and posterior reversible encephalopathy syndrome (PRES)

The iDMC will evaluate safety data and compare the type and frequency of events observed to the type and frequency of events described in the Atezolizumab Investigator's Brochure and enzalutamide local prescribing information. On the basis of this evaluation, the iDMC may recommend that an additional 10 patients be enrolled into the safety run-in portion of the study. Furthermore, the iDMC may request an extension of the observation period until the last patient has completed two cycles (42 days) or an increase in the periodic safety monitoring frequency during the randomized phase of the study.

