#### **5.1.1 Risks Associated with Atezolizumab**

Atezolizumab has been associated with risks such as the following: IRRs and immune-mediated hepatitis, pneumonitis, colitis, myocarditis, pancreatitis, diabetes mellitus, hypothyroidism, hyperthyroidism, adrenal insufficiency, hypophysitis, Guillain-Barré syndrome, myasthenic syndrome or myasthenia gravis, meningoencephalitis, nephritis, and immune-mediated myositis. *Immune-mediated reactions may involve any organ system and may lead to hemophagocytic lymphohistiocytosis and macrophage activation syndrome (considered to be potential risks for atezolizumab).* Refer to Table 3 of the protocol and Section 6 of the Atezolizumab Investigator's Brochure for a detailed description of anticipated safety risks for atezolizumab.

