#### **5.3.1 Adverse Event Reporting Period**

Investigators will seek information on adverse events at each patient contact. All adverse events, whether reported by the patient or noted by study personnel, will be recorded in the patient's medical record and on the Adverse Event eCRF.

**After informed consent** has been obtained **but prior to initiation of study treatment**, only serious adverse events caused by a protocol-mandated intervention (e.g., invasive procedures such as biopsies, discontinuation of medications) should be reported (see Section 5.4.2 for instructions for reporting serious adverse events).

**After initiation of study treatment**, all adverse events will be reported until 30 days after the last dose of study treatment or until initiation of new systemic anti-cancer therapy, whichever occurs first, and serious adverse events and adverse events of special interest will continue to be reported until 90 days after the last dose of study treatment or until initiation of new systemic anti-cancer therapy, whichever occurs first.

Instructions for reporting adverse events that occur after the adverse event reporting period are provided in Section 5.6.

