#### **6.5                SAFETY ANALYSES**

Safety analyses will be performed on the safety-evaluable population, which is defined as all randomized patients from the global enrollment phase who receive any amount of any component of study treatments. Patients will be summarized according to the treatment actually received. Specifically, for patients randomized to the enzalutamide alone arm, if atezolizumab was received by mistake, patients will be grouped under the atezolizumab arm in the safety analyses.

Exposure to study treatment will be summarized to include treatment duration, number of doses, and dose intensity.

Verbatim description of adverse events will be coded to MedDRA preferred terms and graded according to NCI CTCAE v4.0. All adverse events occurring during or after the first study-drug dose will be summarized by treatment arm and NCI CTCAE grade. In addition, serious adverse events, Grade  $\geq$  3 adverse events, adverse events of special

interest (see Section 5.2.2), adverse events leading to treatment discontinuation, and/or modification will be summarized.

Laboratory abnormalities will be summarized by treatment arm and grade.

Changes in selected vital signs will be summarized by treatment arm.

Deaths and causes of death reported during the study treatment period and those reported during the follow-up period after treatment completion/discontinuation will be summarized by treatment arm.

In addition, safety data will be presented in summary tables split by subgroups defined by age, sex, and race/ethnicity, as well as other potential risk factors as appropriate. Additional details will be provided in the SAP prior to performing the analyses.

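### Section 5.2.3 omits hypothyroidism from the events of special interest, so it has no special-interest row and non-serious cases after day 30 are not collected

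*Combined protocol and SAP*

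**What the plan says.** Section 5.2.3 lists the adverse events of special interest, which go to the Sponsor within 24 hours. Its endocrine line reads "Endocrinopathies: diabetes mellitus, pancreatitis, adrenal insufficiency, or hyperthyroidism and hypophysitis".

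Two other sections name the endocrine events. Section 5.1.1, on atezolizumab risks, includes "diabetes mellitus, hypothyroidism, hyperthyroidism, adrenal insufficiency, hypophysitis". Section 3.2, on what the iDMC is to review, gives "i.e., diabetes mellitus, hypothyroidism, hyperthyroidism, adrenal insufficiency, and hypophysitis".

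Special-interest status also decides what is collected and tabulated:

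- **Section 5.3.1.** After treatment starts, "all adverse events will be reported until 30 days after the last dose of study treatment". Serious and special-interest events continue to day 90. Both windows close early if new systemic anti-cancer therapy begins.
- **Section 5.6.** Once the 90-day period has ended, what remains reportable is deaths, plus serious or special-interest events thought to be related to earlier study treatment.
- **Section 6.5.** Special-interest events get their own summary, in addition to the tables of all, serious and Grade 3 or higher events. The pointer there reads "interest (see Section 5.2.2", but 5.2.2 defines serious events.

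Appendix 1 schedules TSH, T3 and T4 on treatment, at the discontinuation visit (within 30 days of the last dose) and at the safety visit (120 ± 30 days). Only patients taking atezolizumab must attend the safety visit.

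On HLH and MAS, Section 5.1.1 says that immune-mediated reactions "may lead to hemophagocytic lymphohistiocytosis and macrophage activation syndrome (considered to be potential risks for atezolizumab". Section 5.2.3 names neither. Its nearest line begins "Events suggestive of hypersensitivity, infusion-related reactions, cytokine-release syndrome, influenza-like illness" and ends with systemic inflammatory response syndrome.

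**The concern.** The same endocrine set appears in Sections 5.1.1 and 3.2. In Section 5.2.3 it appears without hypothyroidism, with pancreatitis placed among the endocrine terms, and no reason is given. The two thyroid outcomes of one drug are therefore handled differently. Hyperthyroidism gets a special-interest row, 90 days of collection and a late route for related cases; non-serious hypothyroidism gets none of these. The protocol orders a late thyroid panel but has no place to record one of the two abnormalities that it can show.

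At stake is how fully a named risk is described in the safety report. The effect is on collection and tabulation only.

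**Working it through.** No sample size, power or alpha figure is involved. The check matches the lists term by term and then traces the missing term through the reporting rules.

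**1. Matching 5.1.1 to 5.2.3.** Section 5.1.1 names 16 associated risks: infusion-related reactions, hepatitis, pneumonitis, colitis, myocarditis, pancreatitis, diabetes, hypothyroidism, hyperthyroidism, adrenal insufficiency, hypophysitis, Guillain-Barré syndrome, myasthenia, meningoencephalitis, nephritis and myositis. Fifteen have an entry in 5.2.3, although myocarditis qualifies only from Grade 2, through the cardiac line. The one without an entry (16 − 15 = 1) is hypothyroidism.

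**2. Tracing a non-serious case by onset (Sections 5.3.1, 5.6, 6.5).**

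| Onset | Hyperthyroidism | Hypothyroidism |
|---|---|---|
| First dose to day 30 after last dose | All-event tables and special-interest summary | All-event tables only |
| Days 31 to 90 | Collected; special-interest summary | Not collected |
| After day 90 | Reported if thought related | No route |

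Serious hypothyroidism is collected to day 90 as a serious event and is not affected by this gap.

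**3. Length of the gap.** The maximum is 90 − 30 = 60 days. If new systemic therapy starts on day t, both windows close at t and the gap is max(0, min(t, 90) − 30). For illustration only, t = 60 gives 60 − 30 = 30 days, and any t up to 30 gives none. The documents give no distribution of t, so only the upper bound can be stated.

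**4. Where the scheduled panels fall.** The discontinuation visit is at day 30 or earlier, inside the all-event window. The safety visit runs from 120 − 30 = day 90 to 120 + 30 = day 150. No post-treatment panel is scheduled on days 31 to 89, so cases in that interval would come to light through symptoms or unscheduled tests. The safety-visit panel matters mainly through Section 5.6: a related, non-serious hyperthyroidism found there can be reported, while a hypothyroidism that began after day 30 cannot. The adverse-event note in Appendix 1 mentions only serious events for this late period, so the special-interest route rests on Section 5.6.

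**5. HLH and MAS.** Section 5.2.2 makes life-threatening, hospitalized and medically significant events serious, and the Table 4 notes add Grade 4 and 5 events. For suspected HLH or MAS, Table 3 specifies permanent discontinuation of atezolizumab, contact with the Medical Monitor and intensive-care monitoring if indicated. I infer that such a case would normally be serious. It would then be collected to day 90, and would enter the serious-event summary and, if on treatment, the discontinuation summary. No section classifies it as always serious. What is missing is a named row in the special-interest summary.

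**6. Patients affected.** The documents give no incidence of late hypothyroidism, so the gap cannot be turned into a patient count.

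**The case against.** The best case for the current text is that 5.2.3 is an urgent-reporting list and need not mirror 5.1.1. It is already selective: Grade 1 myocarditis has a Table 3 entry but falls below the cardiac threshold. Table 3 continues atezolizumab in asymptomatic hypothyroidism, so leaving it off a 24-hour list may be deliberate. That stands as an argument about the 24-hour rule. It does not explain why the same list should also decide 90-day collection, the late route and the summary table. Table 3 also withholds atezolizumab for symptomatic hypothyroidism, as it does for symptomatic hyperthyroidism.

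The endocrine line could be read as illustrative. Other lines in 5.2.3 mark their examples as such (ocular, cardiac and cutaneous events); the endocrine line does not.

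It can also be said that little is lost. Hypothyroidism to day 30 is already tabulated by arm and grade, and the iDMC reviews it. The safety visit is required only in patients taking atezolizumab, so late thyroid ascertainment differs by arm whatever the list says. The Sponsor has decided to close the study for futility, so a change in collection reaches only remaining follow-up. All of this stands, and it is why the point is minor.

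A reader might infer more than the documents support:

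- *That the 90-day collection misses HLH and MAS as known harms.* They are called potential risks, and only a case judged non-serious would be missed.
- *That scheduled panels would detect cases on days 31 to 89 that are then discarded.* No panel is scheduled in that interval.
- *That the special-interest table would be built from the wrong list.* Section 6.5 names serious and special-interest events separately in one sentence, so the pointer to 5.2.2 is clerical.

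**Conclusion.** The inconsistency is real and its severity is minor. One of 16 named atezolizumab risks has no special-interest entry, although two other sections list it with the same endocrine events. The loss is confined to the hypothyroidism row of the special-interest summary, to non-serious cases starting on days 31 to 90 (60 days at most), and to related non-serious cases after that. The general safety tables to day 30 are intact, and OS is unaffected.

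This rests on two assumptions: that the endocrine line is exhaustive as written, and that sites apply the windows in 5.3.1 and 5.6 literally. A reader might infer that the by-arm comparison of hypothyroidism is invalid. That goes too far: up to day 30 it exists for both arms, and beyond day 30 listing the term would improve collection without making ascertainment equal between arms.

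**What to change.** Reconcile Section 5.2.3 with 5.1.1 and 3.2: add hypothyroidism to the endocrine line, so that it falls under the 90-day collection, the Section 5.6 route and the by-arm special-interest summary. If the omission was intended, say so and give the reason.

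The downside is more reports of low-grade hypothyroidism. If these are unwanted within 24 hours, exempt non-serious hypothyroidism from that rule in Sections 5.2.3 and 5.4 and keep it in the collection and the table. Add a table note that the late safety visit is required only in patients taking atezolizumab.

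Two secondary edits: state whether HLH and MAS are to be tabulated as special-interest terms, and change the Section 6.5 cross-reference from 5.2.2 to 5.2.3.

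The cost is a few lines of wording and one table row, plus amendment approval under Section 9.6 and any change to reporting forms. Thyroid panels are already scheduled. Section 6.5 leaves further detail to the SAP, so the table row can be specified there even if the collection change comes too late for most patients.

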### **5.3 METHODS AND TIMING FOR CAPTURING AND ASSESSING SAFETY PARAMETERS**

The investigator is responsible for ensuring that all adverse events (see Section 5.2.1 for definition) are recorded on the Adverse Event eCRF and reported to the Sponsor in accordance with instructions provided in this section and in Sections 5.4.

For each adverse event recorded on the Adverse Event eCRF, the investigator will make an assessment of seriousness (see Section 5.2.2 for serious adverse event criteria), severity (Section 5.3.3), and causality (see Section 5.3.4).

#### **5.3.1 Adverse Event Reporting Period**

Investigators will seek information on adverse events at each patient contact. All adverse events, whether reported by the patient or noted by study personnel, will be recorded in the patient's medical record and on the Adverse Event eCRF.

**After informed consent** has been obtained **but prior to initiation of study treatment**, only serious adverse events caused by a protocol-mandated intervention (e.g., invasive procedures such as biopsies, discontinuation of medications) should be reported (see Section 5.4.2 for instructions for reporting serious adverse events).

**After initiation of study treatment**, all adverse events will be reported until 30 days after the last dose of study treatment or until initiation of new systemic anti-cancer therapy, whichever occurs first, and serious adverse events and adverse events of special interest will continue to be reported until 90 days after the last dose of study treatment or until initiation of new systemic anti-cancer therapy, whichever occurs first.

Instructions for reporting adverse events that occur after the adverse event reporting period are provided in Section 5.6.

### 5.3.2 Eliciting Adverse Event Information

A consistent methodology of non-directive questioning should be adopted for eliciting adverse event information at all patient evaluation timepoints. Examples of non-directive questions include the following:

"How have you felt since your last clinic visit?"

"Have you had any new or changed health problems since you were last here?"

### 5.3.3 Assessment of Severity of Adverse Events

The adverse event severity grading scale for the NCI CTCAE (v4.0) will be used for assessing adverse event severity. Table 4 will be used for assessing severity for adverse events that are not specifically listed in the NCI CTCAE.

**Table 4 Adverse Event Severity Grading Scale for Events Not Specifically Listed in NCI CTCAE**

Grade	Severity
1	Mild; asymptomatic or mild symptoms; clinical or diagnostic observations only; or intervention not indicated
2	Moderate; minimal, local, or non-invasive intervention indicated; or limiting age-appropriate instrumental activities of daily living a
3	Severe or medically significant, but not immediately life-threatening; hospitalization or prolongation of hospitalization indicated; disabling; or limiting self-care activities of daily living b,c
4	Life-threatening consequences or urgent intervention indicated d
5	Death related to adverse event d

NCI CTCAE = National Cancer Institute Common Terminology Criteria for Adverse Events.

Note: On the basis of the most recent version of NCI CTCAE (v4.0), which can be found at [http://ctep.cancer.gov/protocolDevelopment/electronic\\_applications/ctc.htm](http://ctep.cancer.gov/protocolDevelopment/electronic_applications/ctc.htm)

a Instrumental activities of daily living refer to preparing meals, shopping for groceries or clothes, using the telephone, managing money, etc.

b Examples of self-care activities of daily living include bathing, dressing and undressing, feeding oneself, using the toilet, and taking medications, as performed by patients who are not bedridden.

c If an event is assessed as a "significant medical event," it must be reported as a serious adverse event (see Section 5.4.2 for reporting instructions), per the definition of serious adverse event in Section 5.2.2.

d Grade 4 and 5 events must be reported as serious adverse events (see Section 5.4.2 for reporting instructions), per the definition of serious adverse event in Section 5.2.2.

